### **Background:**

The past 30 years, laser lithotripsy during ureteroscopy (URS) has been performed using Holmium: yttrium-aluminum-garnet laser (Ho:YAG). The Ho:YAG has been considered the *gold-standard* laser for URS because of its versatility, with the ability to break all kinds of stones in the urinary tract as well as tumor- and soft tissue ablation. Development of higher power laser technology has allowed the limits of what can be achieved with URS to be set even higher . In comparison to stone fragmentation, techniques such as dusting and popcorning often implement higher power settings (>20 W), and the efficacy associated with different strategies has been the focus of many studies . In recent times, the intraoperative safety of URS has gained increasing attention, particularly with regard to high intra-pelvic pressure (IPP) and raised temperature levels . The results of such studies include new recommendations for procedural techniques aimed at reducing the risk of complications. One such example is the avoidance of pressurized irrigation pumps . Recently, a new Thulium fiber laser (TFL) has been introduced. With the advent of the TFL, discussion surrounding high temperatures during lithotripsy and resultant thermal damage have been fueled further . Defining safe margins for laser settings is especially important for the TFL as no consensus exists for what is acceptable during URS. In a recent publication, some experts' preferred settings for the TFL during URS were presented, and a variety of different settings was suggested included high power settings as high as 45 Watts . Earlier this year we investigated temperature profiles during URS laser activation with different lasers (TFL and Ho:YAG), laser settings and fiber sizes in a pre-clinical study . We found that the rise in temperature in the renal pelvis was negligible when low settings below 8 Watts were used, even when the laser was activated continuously for 180 seconds. However, applying laser settings of 20 Watts resulted in a significant rise in temperature and the threshold for heat induced cell injury (43°C) was reach and trespassed after approximately 40-45 seconds of continuous laser activation depending on the size of the fiber. Using smaller fiber extended the time before 43°C was reached. These findings need to

be confirmed in clinical studies. However, until then, we expect laser settings  $\leq$  20 Watts for lithotripsy in the renal pelvis to be safe with regards to temperature.

To date, there are no clinical studies investigating intrarenal temperatures during URS laser treatment. Studying temperature profiles during URS laser activation in patients is therefore of critical importance and highly clinically relevant to define the safety of different laser settings and power.

### **Aims of the study:**

The primary aim of this study is to investigate the temperature profiles in the renal pelvis during TFL laser activation using different settings. To this end, comparison of peak temperatures during laser activation for different settings is the main aim. Secondary aim is trying to define the duration of safe laser activation until the threshold for heat induced cell injury ( $43^{\circ}\text{C}$ ) is reached.

### **Hypothesis:**

1. Laser activation using low settings is safe regarding intrarenal temperature.
2. The peak temperature in the renal pelvis is higher when high power settings are used compared to when lower settings are used.  $H_0$ : *"There is no difference in peak temperatures in the renal pelvis regardless of the laser settings used."*
3. The time before  $43^{\circ}\text{C}$  of intrarenal temperature is reached is longer for low laser settings (if  $43^{\circ}\text{C}$  is reached at all) compared to high settings. The corresponding  $H_0$  is that *"there is no difference in time until  $43^{\circ}\text{C}$  is reached following laser lithotripsy with high and low laser settings."*

### **Study design:**

The study is planned as a prospective clinical trial.

### **Patients and data sampling:**

Patients  $\geq$  18 years with a ureteral stone (with or without a concomitant renal stone) and an indwelling nephrostomy tube scheduled for URS lithotripsy at the day surgery unit at HUH, are invited to be enrolled in the study. Due to the result of the pre-clinical study, a power analysis reveals that a total of 10 patients are considered sufficient for inclusion in the study.

The following data need to be registered:

- *Preoperative status:* Age, sex, ASA-status, comorbidity, indication for surgery, stone status, infection.
- *Peroperative characteristics:* Primary surgeon, antibiotic prophylaxis, operative time, need for safety guide wire, type of endoscope (semi-rigid/flexible), balloon dilatation, impacted stone, successful access to the stone, laser settings, laser time and energy used, temperature measurements, retrieval of fragments or left for spontaneous passage, surgeon's assessment of post endoscopic stone free status, complications, placement of JJ-stent.
- *Postoperative status:* Length of hospital stay, immediate complications that need urgent treatment, complications after discharge requiring readmission, 3-months follow-up with CT scan (SFR, stricture rate).

The data will be plotted in electronical registration forms. Completed registration-forms are exported to a SPSS database for statistical analyses.

The registration-forms and the database will be stored at Helse-Bergen's research server in a designated file assigned from the Data Protection Officer. An ID-Key file combining personal ID to the registration form will be stored at a designated server for this purpose at Helse-Bergen's research servers. Only the project manager ([name]) will have access to this ID-Key file.

The registration forms and the ID-Key file will be kept on the server for five years after the study has been completed in accordance with the law. After five years the data will be made anonymous in terms of deleting the ID-Key file.

#### **Power analysis:**

In the pre-clinical study, we found that the peak temperatures when activating the TFL laser continuously for 180 seconds using a 150 $\mu$ m fiber were 26.7°C, 32.8°C and 45.2°C for the laser settings of 0.4J/6Hz (2.4W), 0.8J/10Hz (8W) and 0.2J/100Hz (20W), respectively . The

corresponding baseline temperature before activating the laser were 24.1°C, 24.5°C and 25.3°C.

We expect both the baseline and the peak temperatures to be approximately similar also during URS in real patients as the temperature of the irrigational fluid is the same as in the pre-clinical study (23 °C) .

Peak temperatures for different laser settings will be compared using paired-samples *t*-test. Using the peak temperatures for the different laser settings found in the pre-clinical study, the sample size can be calculated for the clinical study assuming the peak temperature will be similar. As the peak temperatures for different laser settings will be compared within the same individual, paired samples *t*-test is used. The total number of patients required for comparison is therefore lower than if peak temperatures were measured for only one laser setting in each patient. In that case independent samples *t*-test would have been the correct test for comparison.

The effect size is calculated to be 4.4 comparing peak temperatures at 2.4W and 8W, and 2.9 comparing peak temperatures at 8W and 20W. The assumed peak temperatures for 2.4W, 8W and 20W are 26.7°C, 32.8°C and 45.2°C, respectively. The corresponding standard deviations are assumed to be 0.8, 1.6 and 4.9, respectively. The  $\alpha$  error probability is set to 0.05 and the power (1- $\beta$  error probability) is set to 0.8.

Using G\*Power, version 3.1.9.4 and IBM SPSS Statistics 27 for power analysis, the total sample size is calculated to be 3 when comparing 2.4W and 8W and 4 when comparing 8W and 20W. The highest number of these two calculations is considered appropriate to use. To compensate for possible non-evaluable patients, a total of 10 patients are planned for inclusion in the study.

### **Statistical analyses:**

Statistical analyses will be performed using IBM SPSS Statistics 27 or higher (IBM, Armonk, NY). A *p*-value < 0.05 will determine statistical significance.

Peak temperatures between different laser settings will be compared using paired-samples *t*-tests. Wilcoxon test for related samples will be used comparing the continuous temperature profiles for different laser settings. Exact  $\chi^2$ -test test and Fisher's Exact test are used comparing categorical variables.

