Laser disintegration of the stone is started using the lowest laser setting of 5W continuously for 120 seconds followed by 60 seconds of idling laser. Temperature measurements are maintained continuously during these 180 seconds, with two measurements per second. When the temperature in the renal pelvis has reached base temperature after one series of measurements, the procedure is repeated for the next laser setting. In total, URS lithotripsy are performed for three different settings. If 43°C is reached during laser activation for any of the laser settings, the laser will be stopped immediately and further laser activation with that specific settings will be aborted. Laser activation with subsequent settings will be ready when base temperature is reached.

If stone treatment is not completed at the end of the three series of laser activation and temperature measurements, further stone disintegration will be performed before finishing the URS procedure. A JJ-stent is placed at the end if deemed necessary by the surgeon. The nephrostomy tube is removed when considered appropriate. If a JJ-stent is placed after the procedure, this is removed according to standard routine after 1-2 weeks in the outpatient clinic. Follow-up with CT is performed at 3 months post endoscopically for all patients to assess stone free status and exclude a ureteral stricture in addition to a clinical consultation.

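### Minor: one peak-temperature null is tested by several unadjusted paired t-tests, with no list of pairs and no rule for rejecting it

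*Combined protocol and SAP*

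**What the plan says.** - **Aim** (Aims of the study): "comparison of peak temperatures during laser activation for different settings is the main aim".
- **Hypothesis 2** (Hypothesis) is directional: "The peak temperature in the renal pelvis is higher when high power settings are used compared to when lower settings are used". Its null is a single statement over all settings, without direction: "There is no difference in peak temperatures in the renal pelvis regardless of the laser settings used".
- **Test** (Statistical analyses): "Peak temperatures between different laser settings will be compared using paired-samples" t-tests, in the plural. The only criterion is a p-value below "0.05 will determine statistical significance". No overall test, pair list, testing order, adjustment or sidedness is given.
- **Pairs.** The only pairs named anywhere are in the Power analysis, where they serve the sample size: "the total sample size is calculated to be 3 when comparing 2.4W and 8W and 4 when comparing 8W and 20W". Each uses alpha 0.05 and power 0.8, and 10 patients are then planned.
- **Number of settings.** The URS procedure section says "In total, URS lithotripsy are performed for three different settings", which allows three pairs. The Laser settings section describes four series, which allows six. It names 2.4, 8, 20 and 30 W in its text but 5, 10, 20 and 30 W in its list. The Power analysis uses 2.4, 8 and 20 W.

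**The concern.** A single null needs a single rule for rejecting it. Here several tests bear on the same null, each at 0.05, and the plan does not say how their results combine. If one significant pair is enough, the chance of wrongly rejecting the null exceeds 5% and grows with the number of pairs tested. That number is open, because the pairs are not listed and the sections disagree on the settings.

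What is at stake is limited: one isolated p just under 0.05 could be reported as a real difference between settings. This can be inflated only where two or more of the tested comparisons are truly null.

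**Working it through.** **1. Reproduce the plan's sample size.** Inputs from the Power analysis: peaks 26.7, 32.8 and 45.2°C; "The corresponding standard deviations are assumed to be 0.8, 1.6 and 4.9, respectively"; alpha 0.05; power 0.8. The within-patient correlation r is not stated; r = 0.5 reproduces both effect sizes.

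dz = mean difference / √(s₁² + s₂² − 2·r·s₁·s₂)

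- 2.4 W v 8 W: 6.1 / √(0.64 + 2.56 − 1.28) = 6.1 / 1.386 = 4.40 (stated 4.4)
- 8 W v 20 W: 12.4 / √(2.56 + 24.01 − 7.84) = 12.4 / 4.328 = 2.87 (stated 2.9)

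Paired-t power, from the noncentral t with n − 1 degrees of freedom and noncentrality dz·√n:

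- dz 4.4, two-sided: 94% at n = 3, so N = 3, as stated.
- dz 2.9, two-sided: 72% at n = 3 and 96% at n = 4, so N = 4, as stated.
- dz 2.9, one-sided: 92% at n = 3, so N would be 3.

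The stated N of 4 therefore fits two-sided tests only.

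**2. False rejection when all settings are equal.** For two independent tests, 1 − 0.95² = 9.75%. The pairs share a setting, so this was simulated: n = 10, normal peaks, two-sided 0.05, the plan's SDs (4.9 assumed for a fourth setting) or equal SDs, r from 0 to 0.8. A rejection means at least one p<0.05.

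| Pairs tested | Unadjusted | Holm |
|---|---|---|
| Two powered pairs | 9–10% | 4.7–5.0% |
| Three settings, all 3 pairs | 10–13% | 3.6–4.7% |
| Four settings, 3 adjacent pairs | 13–14% | 4.5–4.8% |
| Four settings, all 6 pairs | 17–22% | 3.4–4.6% |

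At r = 0.9 with the plan's SDs, the two-pair figure falls to about 8.6–8.8% and the six-pair figure to about 16%.

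If both powered pairs had to be significant, the rate is about 0.2–1.2%. Counting only false positives in the direction of hypothesis 2, it is about 5% for two pairs and 9–12% for six.

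**3. False rejection when only some settings are equal** (four settings; Holm applied over the null pairs only):

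| Truth | Unadjusted | Holm |
|---|---|---|
| Three settings equal, one different, all six pairs tested | 10–13% | 3.6–4.7% |
| Lowest two equal and highest two equal | 9.5–10% | about 5% |
| Only the top pair equal | about 5% | about 5% |

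**4. Cost of Holm in power.** Effect size 2.9, same noncentral-t formula, at Holm's strictest step (0.05 divided by the number of listed pairs):

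| Evaluable patients | No adjustment | 2 pairs (0.025) | 6 pairs (0.0083) |
|---|---|---|---|
| 4 | 96% | 85% | 54% |
| 5 | 99.6% | 98% | 84% |
| 6 | >99.9% | 99.7% | 97% |
| 10 | >99.9% | >99.9% | >99.9% |

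**5. What the figures leave out.** The laser is stopped at 43°C, and the simulated peaks ignore this. Under the Power analysis mean and SD, P(20 W peak ≥ 43) = 1 − Φ((43 − 45.2)/4.9) = 1 − Φ(−0.449) = 67%. That mean comes from 180 seconds of pre-clinical activation at 0.2 J/100 Hz. The clinical sections plan 120 seconds and list 0.5 J/40 Hz for 20 W, so 67% is only indicative. The error rates are least reliable for pairs involving 20 W or more.

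**The case against.** **The 9–10% rests on a rule the plan does not state.** This stands. The Power analysis sizes both pairs and takes the larger number, which is compatible with requiring both steps to be significant; the rate is then about 1% or less. The plan states neither rule, and that is the gap.

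**Sidedness is not really open.** This stands: the stated N of 4 implies two-sided tests. A reader might infer from the directional hypothesis that one-sided tests are intended, but the plan's own arithmetic does not support that. It is still worth one word in the analysis section.

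**The expected effects are far too large for this to matter.** This largely stands. With peaks of 26.7, 32.8 and 45.2°C neither powered pair is null, and both would survive adjustment. But these values come from a pre-clinical model, and the Power analysis assumes no peak for 30 W.

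**Where a tie is most plausible, Holm does nothing.** This stands. If only the top two settings give equal peaks, for example because both are cut off at 43°C, just one comparison is null and the rate is about 5% either way.

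**A 10-patient study is exploratory.** This carries less weight, because the plan sets a formal null, an alpha, a power and a significance criterion. Holm is one reasonable choice; an overall test or a fixed testing order would also close the gap.

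**Conclusion.** The point holds as a minor, conditional one. The plan has one null, several unadjusted tests and no rejection rule. If any one significant pair is enough and all settings are truly equal, false rejection with 10 patients is about 9–10% for the two powered pairs (8.6–8.8% if r is near 0.9), 10–13% for all three pairs of three settings, and about 16–22% for all six pairs of four. These figures assume normal peaks, two-sided tests and no effect of the 43°C stop.

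Two stronger readings are not supported. A reader might infer that the trial runs at an error rate near 20%; no section says that all six pairs will be tested. A reader might also infer that the main result is unreliable; the contrasts the plan expects would stay significant after adjustment.

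**What to change.** First reconcile the number and wattage of the settings across the Power analysis, the URS procedure section and the Laser settings section; the pair list cannot be fixed until then. Keep the paired t-tests and add to the Statistical analyses section:

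> The confirmatory pairs are [list, for example adjacent settings]. Tests are two-sided. P-values are Holm-adjusted across these pairs. The null of hypothesis 2 is rejected only if at least one adjusted p is below 0.05, and a pair is called different only if its own adjusted p is below 0.05.

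The change needs a few sentences and simple arithmetic on the p-values that SPSS prints, with no extra patients or data. The price is power if few patients are evaluable, as the table in step 4 shows, so keep the list short. Holm does not deal with peaks capped by the 43°C stop; that is a separate issue.

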### **Ethical considerations, ethical approval, and patient consent**

TFL is emerging as the laser of choice for ureteroscopic lithotripsy, and the laser has been demonstrated to be superior to the current gold-standard Ho:YAG laser regarding clinical outcomes. Despite being in daily use around the world, no consensus exists of what is considered the preferred laser settings and different experts recommend a variety of suggestions. Some of the laser settings preferred by experts exceeds 20W, which are settings found to be associated very high temperatures (> 43°C). Defining safe laser settings with regard to temperatures therefore seems to be highly clinically relevant. The intra renal temperature is measured continuously during laser activation in the planned study, and laser activation is stopped immediately if the temperature reach 43°C for any laser setting. Participating in this study should therefore not expose the patients to extra risk of harm. The operative time will be extended by approximately 10 – 15 minutes for the patients in whom the ureteral stones *cannot* be pushed back into the renal pelvis for disintegration as the stone must be disintegrated in the ureter *before* temperature measurements can be performed in the renal pelvis in such patients. However, as the URS procedures are performed in general anaesthesia, the extra time caused by the temperature registration is not considered to cause any disadvantage for these patients.

Applications for approval by The National Committees for Research Ethics in Norway and The Data Protection Authorities at HUH will be sent prior to study start. In addition, the study will be registered in the clinical research database for randomized trials, ClinicalTrials.gov.

All patients eligible for inclusion in the study will receive oral and written information. Participation in the study is voluntarily, and the patient can choose to withdraw at any point during the study process. Inclusion in the study will only be done after the consent form is signed. The patient information and consent form used for this purpose is obtained from The National Committees for Research Ethics in Norway's website ([https://helseforskning.etikkom.no/frister/malforinformasjonsskriv?p\\_dim=34672](https://helseforskning.etikkom.no/frister/malforinformasjonsskriv?p_dim=34672)).

### **The URS procedure and follow-up**

Only patients with ureteral stones or combined ureteral and renal stones and who has an indwelling nephrostomy catheter are eligible for inclusion in the study.

The URS procedure is performed in general anaesthesia and all patients will have prophylactic antibiotics prior to surgery start, either according to urine culture or current local regime.

The procedure starts with a cystoscopy followed by semirigid URS when considered appropriate. Balloon dilatation is performed on demand. When reaching the stone, this is flushed back into the renal pelvis for disintegration there if possible. In cases where the stone cannot be flushed back into the renal pelvis, the stone is disintegrated in situ before the endoscope is advanced up to the renal pelvis for temperature measurements. Before laser disintegration, the semirigid ureteroscope is changed for a flexible ureteroscope (Olympus V3) that is advanced to the renal pelvis directly or over a guide wire that must be removed as soon as the endoscope is in place. An access sheath cannot be used during this study. Room-tempered (23°C), gravitational irrigation fluid at 60 cm height is used throughout the procedure. Manual pumping should be avoided and should in any case not be performed during the temperature measurements. Under endoscopic vision, a sterilized thermocouple sensor (K-type, same as in the pre-clinical study) is introduced through the nephrostomy tube so that the tip can be identified through the side-holes of the nephrostomy tube. The sensors have undergone sterilization. Formal testing by the microbiological department at Haukeland University Hospital has verified this process successfully sterilizes the sensors. The stone is moved to the central renal pelvis for laser disintegration, and a 150µm laser fiber is introduced into the renal pelvis through the working channel of the flexible ureteroscope. At this point the nephrostomy tube is clamped to achieve filling of the renal pelvis and to mimic a normal procedure.

Laser disintegration of the stone is started using the lowest laser setting of 5W continuously for 120 seconds followed by 60 seconds of idling laser. Temperature measurements are maintained continuously during these 180 seconds, with two measurements per second. When the temperature in the renal pelvis has reached base temperature after one series of measurements, the procedure is repeated for the next laser setting. In total, URS lithotripsy are performed for three different settings. If 43°C is reached during laser activation for any of the laser settings, the laser will be stopped immediately and further laser activation with that specific settings will be aborted. Laser activation with subsequent settings will be ready when base temperature is reached.

If stone treatment is not completed at the end of the three series of laser activation and temperature measurements, further stone disintegration will be performed before finishing the URS procedure. A JJ-stent is placed at the end if deemed necessary by the surgeon. The nephrostomy tube is removed when considered appropriate. If a JJ-stent is placed after the procedure, this is removed according to standard routine after 1-2 weeks in the outpatient clinic. Follow-up with CT is performed at 3 months post endoscopically for all patients to assess stone free status and exclude a ureteral stricture in addition to a clinical consultation.

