### **Laser settings**

After reaching the renal pelvis with the flexible ureteroscope, the 150µm laser fiber is inserted through the working channel of the scope. The laser is then activated for 120 seconds starting with the lowest settings. Temperature registration is then continued for another 60 seconds. When the temperature in the renal pelvis has returned to basic, the registration is repeated for the next laser settings. A total of 4 series is performed with different laser settings (2.4W, 8W, 20W and 30W) with 150µm laser fiber. Laser activation is immediately paused if the registered temperature reach 43°C. The following laser settings will be used in the study:

**5 watts of power:** 0.5 J / 10 Hz, short pulse

**10 watts of power:** 0.5 J / 20 Hz, short pulse

**20 watts of power:** 0.5 J / 40 Hz, short pulse

**30 watts of power:** 1 J / 30 Hz, short pulse

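### The plan expects settings up to 20 W to be thermally safe and claims no extra risk, but its own figures predict 43°C at 20 W in most patients, who may then go on to a further setting

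*Combined protocol and SAP*

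**What the plan says.** All references are to the combined protocol and SAP.

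- **Background, safety expectation.** Pending clinical confirmation, the authors expect settings at or below "20 Watts for lithotripsy in the renal pelvis to be safe with regards to temperature". No activation time is attached.
- **Background, bench result.** The section also reports that "applying laser settings of 20 Watts resulted in a significant rise in temperature and the threshold for heat induced cell injury" (43°C) was reached and exceeded after about 40-45 s of continuous firing, depending on fiber size.
- **Power analysis.** The bench peak at 20 W was 45.2°C over 180 s with the 150 µm fiber, from a baseline of 25.3°C. The SD is taken as 4.9. Baseline and peak are expected to be about the same in patients.
- **The URS procedure and follow-up.** Each setting is fired continuously for 120 s, starting at 5 W, with two temperature readings per second. If 43°C is reached, "the laser will be stopped immediately and further laser activation with that specific settings will be aborted". Then: "Laser activation with subsequent settings will be ready when base temperature is reached". The section counts three settings in total.
- **Laser settings.** "The laser is then activated for 120 seconds starting with the lowest settings". Then: "A total of 4 series is performed with different laser settings (2.4W, 8W, 20W and 30W) with 150µm laser fiber". The list beneath that sentence gives 5, 10, 20 and 30 W, the last as "1 J / 30 Hz, short pulse". At 43°C, firing is here said to be paused.
- **Ethical considerations.** Settings above 20 W are linked to temperatures over 43°C. Continuous measurement and the immediate stop are then described, and the section concludes: "Participating in this study should therefore not expose the patients to extra risk of harm".

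**The concern.** Read together, these statements do not describe one safety position. The Background places 20 W on the safe side of the line and the ethics section places the thermal problem above 20 W. The bench result and the sample-size assumption both put 20 W itself past 43°C, well within the planned firing time.

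The stop rule acts on one setting at a time. Settings run from lowest to highest, so any setting that follows a stopped one has higher power. No section says whether a patient who has reached the threshold should go further, other than that base temperature must first be regained.

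The no-extra-risk sentence is the plan's stated justification for these activations. It leaves out two facts that follow from the rest of the document: the stop is expected to be needed at 20 W, and the patient may then continue. Anyone judging the risk from the Background and ethics sections would take reaching 43°C at 20 W to be unexpected.

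**Working it through.** **Step 1. Confirm that the plan uses the bench values as patient assumptions.** The Power analysis compares 8 W (32.8°C, SD 1.6) with 20 W (45.2°C, SD 4.9). With a within-patient correlation of 0.5 (my assumption; none is stated), the paired effect size is

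(45.2 − 32.8) / √(1.6² + 4.9² − 2 × 0.5 × 1.6 × 4.9) = 12.4 / √18.73 = 2.87,

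against 2.9 stated. A two-sided paired t-test at 0.05 then needs n = 4 (power 0.958 at 2.9), as the plan says. The comparison of 2.4 W with 8 W gives 4.40 and n = 3, also as stated. So a mean of 45.2°C with SD 4.9 is what the plan expects in patients at 20 W.

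**Step 2. Compare firing time with bench time to threshold.** 120/45 = 2.7 and 120/40 = 3.0. The planned firing lasts about 2.7 to 3 times as long as 20 W took to reach 43°C on the bench.

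**Step 3. Chance of reaching 43°C, taking uncapped peaks as normal.** P = 1 − Φ((43 − mean)/SD).

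| Setting | Mean (SD), °C | P(peak > 43°C) |
|---|---|---|
| 2.4 W | 26.7 (0.8) | about 0 |
| 8 W | 32.8 (1.6) | about 0 |
| 20 W | 45.2 (4.9) | 1 − Φ(−0.449) = 0.67 |

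Among 10 patients that is 10 × 0.673 = 6.7 expected. Treating patients as independent, the chance that at least 5 of 10 reach 43°C is 0.93.

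**Step 4. Sensitivity to the 20 W mean, SD kept at 4.9.**

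| True mean, °C | P(peak > 43°C) |
|---|---|
| 41 | 0.34 |
| 43 | 0.50 |
| 44 | 0.58 |
| 45.2 (plan) | 0.67 |

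**Step 5. Does 120 s rather than the bench 180 s matter?** Take T = 25.3 + A(1 − exp(−t/τ)) through 43°C at 40 or 45 s and 45.2°C at 180 s. This gives τ of 18.2 or 20.4 s, A of 19.9°C, and 45.1-45.2°C at 120 s. Under this assumed curve the shorter firing barely changes the peak. The Background does not say which end of 40-45 s belongs to the 150 µm fiber, so both were used.

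**Step 6. What follows after 43°C.** The two procedural sections differ on three points:

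| Point | The URS procedure and follow-up | Laser settings |
|---|---|---|
| Number of settings | three | four series |
| Powers | starts at 5 W | 2.4/8/20/30 W in the text, 5/10/20/30 W in the list |
| At 43°C | that setting is aborted | firing is paused |

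If the three settings were 5, 10 and 20 W, no patient would go past 20 W. If there are four series, 30 W follows 20 W. The text does not settle this, and the documents quote no bench figure for 30 W.

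**The case against.** The strongest reply is that the plan controls the hazard. Temperature is read twice a second, firing stops at once at 43°C for every setting, and the pelvis must return to base temperature before the next series. Time to 43°C is the declared secondary aim, so reaching it is foreseen, and the ethics section openly links settings above 20 W to temperatures over 43°C. All of this stands. It limits exposure within a series. It does not make the Background agree with its own bench result, and it does not address continuing upward after a stop.

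It can also be said that the Background gives no activation time, so its expectation may concern shorter or intermittent firing, and that the bench 20 W was 0.2 J/100 Hz whereas the trial uses 0.5 J/40 Hz. Both are fair limits on the 67%. The planned firing is nevertheless continuous for 120 s, and the plan itself carries the bench peaks over to patients.

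A reader might infer more than the documents support:

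- **That most patients will be taken from 43°C at 20 W to 30 W.** The count of three or four settings is unresolved.
- **That 20 W is the plan's upper safety limit.** The Background is silent above 20 W.
- **That heating at 30 W can be predicted.** Three bench points with different pulse settings do not support an extrapolation.
- **That patients were told something wrong.** The consent pages are not among the material reviewed.
- **That a study-wide stopping rule is missing.** That would be an added safeguard; its absence is not a contradiction in the text.

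**Conclusion.** The point holds as an internal contradiction in the safety premise. On the plan's own mean and SD, reaching 43°C is the expected result of a 20 W series: about 67%, or roughly 7 of 10 patients. The Background calls such settings safe, and the ethics section concludes that there is no extra risk without mentioning this expectation or the possible continuation to a further setting.

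The 67% assumes normal peaks, bench values that apply to patients, and equivalence of the two 20 W pulse settings. With a true mean of 41-44°C it falls to 34-58%, so the word most depends on the plan's own mean being about right. Even the lowest of these is about one patient in three.

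The documents do not show that the stop fails, nor that escalation to 30 W is certain. The procedural sections leave that step open, and this is itself part of the defect.

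**What to change.** 1. **Background.** Correct the sentence on settings up to 20 W so that it agrees with the bench time to 43°C and with the Power analysis peak, for the planned 120 s of continuous firing.
2. **Ethical considerations.** Qualify the no-extra-risk sentence. State that, on the plan's own figures, most 20 W series are expected to reach 43°C and be stopped, and that the patient may then proceed to a further setting. Keep the description of the stop and the cooling.
3. **The URS procedure and follow-up, and Laser settings.** Reconcile the number of settings (three or four), the list (2.4/8/20/30 W or 5/10/20/30 W), aborting versus pausing, and what follows for a patient who has reached 43°C. The result must be consistent with the ethics section.

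The sponsor and ethics committee decide the clinical rule; this review does not propose one. The cost is wording in four sections. Whether the number of series per patient changes depends on their decision.
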